3.4 Randomization and Blinding

Prior to randomization, participants completed baseline data collection and received the healthy food prescription. Researchers randomized participants to either the FoodRx (n=299) or comparison (n=297) group with a 1:1 allocation ratio using a computer-generated, concealed, blocked randomization sequence in REDCap (Research Electronic Data Capture)⁴¹ created by an independent statistician. Blocking variables included gender identity (woman, man), recruitment location (urban setting, rural setting, Indigenous primary care clinic), and baseline A1C (6.5-8.5%, 8.6-12%). The intervention group received both a healthy food prescription and a healthy food incentive. The comparison group received a healthy food prescription alone.

Due to the nature of the intervention, participants were not blinded to their allocation; however, they were blinded to study objectives. Participants in the comparison group were also blinded to the details of the healthy food incentive, including its monetary value and eligible foods. Care providers and researchers who collected and analyzed the data were blinded to treatment allocation with the exception of a research assistant who assisted participants in the intervention group throughout the trial.

4. Trial Population

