4.1 Recruitment, Eligibility Criteria, and Screening

From May 2021 to December 2023, research assistants recruited participants through primary care clinics and community organizations (e.g., food banks) in urban and rural locations throughout the province of Alberta, Canada.

Adults aged 18-85 years with T2DM were eligible to participate if they: 1) had persistent hyperglycemia, defined as an A1C between 6.5-12% at baseline (0 months); blood glucose levels below 6.5% are considered clinically acceptable and those above 12% require urgent anti-hyperglycemic treatment with insulin, 2) experienced household food insecurity in the past 6 months, indicated by answering affirmatively to at least one question on Health Canada's Household Food Security Survey Module (HFSSM)⁴³, 3) spoke English or had someone to assist them during the study, and 4) were willing to travel to Calgary or Edmonton to complete data collection if they were not referred by a primary care clinician

Exclusion criteria included significant diabetes complications (i.e., intensive insulin therapy, current metabolic decompensation, diabetic ketoacidosis and/or hyperglycemic hyperosmolar emergency within the past year, recurrent severe hypoglycemia within the past 3 months, hypoglycemic unawareness), and conditions that may have influenced typical dietary patterns (i.e., pregnancy, breastfeeding, diagnosed eating disorder). Participants were excluded if they resided in a facility that provided meals (e.g., retirement home), were participating in other clinical trials that might interfere with the FoodRx program, did not have ongoing and reasonable access to

study-affiliated supermarkets, planned to leave Canada for more than 2 weeks at a time during the intervention, and/or had other household members that participated in the study.

Researchers assessed eligibility at baseline (0 months) using a screening questionnaire and participants indicated their informed consent to participate prior to beginning baseline data collection.

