4.2 Sample Size

The sample size calculation was based on A1C, the primary outcome for the RCT. A mean baseline A1C of 8.5% (SD=1.4%) was expected in our population based on local administrative data.⁴⁴ For 90% power to detect a minimally important clinical difference in A1C of 0.5%⁴⁵, 594 participants were required assuming 5% type 1 error, 30% attrition⁴⁶, and potential design effects based on sampling in different primary care clinics and communities (25% inflation).

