6.1 Regression Model Assumptions

We will assess whether the assumptions for each regression model are met, and will take appropriate corrective steps if violations are identified. In analyses where the proportional-odds assumption is violated, we will use generalized proportional odds models to preserve the ordinal nature of the outcome(s) in question and allow covariate effects to vary across thresholds as necessary. In analyses with severe violations, we will use multinomial logistic regression models.

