6.2 Hypothesis Testing

For hypothesis testing, confidence intervals are set at 95% and statistical significance is set at $p < 0.05$. Confidence intervals and absolute p-values will be reported in all manuscripts, regardless of statistical significance. Adjusted and unadjusted estimates will be reported.¹⁰⁸ When interpreting results, emphasis will be placed on effect sizes, confidence intervals, and clinical relevance rather than statistical significance alone.

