7.4 Primary Manuscript

This paper will report results for 12-month A1C, our primary outcome, along with secondary and exploratory outcomes at 6-, 12-, and/or 18-months, including blood glucose levels, clinical health markers, and need for antihyperglycemic medication.

12-month A1C, Primary Outcome

We will assess the intention to treat effect of group assignment on mean A1C at 12-months as a continuous outcome using mixed-effects linear regression. The primary test will be the group \times time interaction contrast at 12-months (i.e., post-intervention), which estimates between-group differences in mean A1C from baseline to 12 months. Models will be adjusted for baseline A1C to estimate treatment effect while holding baseline A1C constant, and additional blocking variables (gender, recruitment location). To improve the precision of effect estimates, models will also be adjusted for age, race/ethnicity, educational attainment, number of children living in the home, and diabetes duration. Additionally, all models will include a data source indicator variable (study measured vs administrative health data), group (FoodRx vs comparison), collection timing (number of days measurement was taken since baseline), and restart cohort indicator variable (did not restart vs did restart). We will include random intercepts for participants (participant study ID) to account for within-subject correlation due to repeated measures, and for primary care clinics (clinic study ID) to account for clustering of participants within clinics. Missing data for covariates will be addressed using full information maximum likelihood.

We will conduct subgroup analyses for 12-month A1C by baseline household food insecurity severity (marginal, moderate, severe), gender (man, woman, gender diverse), recruitment location (urban setting, rural setting, Indigenous primary care clinic), Indigenous identity, baseline A1C ($\leq 8.5\%$, $\geq 8.6\%$), and baseline insulin use (no, yes).

We will conduct dose-response analyses to examine whether 12-month A1C differs based on the total value of incentives redeemed, a continuous variable, in the first 6 months for the mid-intervention analysis, and in the full 12-months for the post-intervention analysis.

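### The primary A1C model rests on a participant random intercept with no residual covariance or robust standard error, so the 12-month test can exceed 5% if A1C correlation weakens between visits

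*SAP*

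**What the plan says.** SAP section 7.4 analyses 12-month A1C by mixed-effects linear regression. The primary test is the group-by-time contrast at 12 months, described as a between-group difference from baseline to 12 months. The model is also adjusted for baseline A1C. Within-subject dependence is handled in one sentence: "We will include random intercepts for participants (participant study ID) to account for within-subject correlation due to repeated measures". A second random intercept is for clinic.

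No residual covariance, random slope or robust standard error is named. None of the six additional sensitivity analyses listed for this outcome varies the covariance. Section 6.1 says the team "will take appropriate corrective steps if violations are identified", but spells out a remedy only for the proportional-odds assumption. The same random-intercept sentence recurs for the other continuous repeated-measures outcomes in sections 7.4 to 7.9.

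On variability, section 4.2 gives one figure: "A mean baseline A1C of 8.5% (SD=1.4%) was expected in our population". No follow-up SD and no between-visit correlation appear anywhere.

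**The concern.** A participant intercept with independent residuals is compound symmetry. The fitted model averages variances and covariances over all visits and applies the average to month 12. If month 12 is less predictable from baseline than month 6 is, the average understates the uncertainty at month 12. The confidence interval is then too narrow and the p-value too small.

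Some weakening of correlation over a year is plausible, because section 4.3 lets providers adjust glycaemic medication throughout. What is at stake is the error rate of the one test that section 6.5 treats as the basis for inference when it declines multiplicity adjustment.

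**Working it through.** **Inputs from the SAP.** Section 3.4: "FoodRx (n=299) or comparison (n=297) group with a 1:1 allocation ratio", so 596 in total. Section 4.2: SD 1.4, difference 0.5, 90% power, 5% type I error, 30% attrition, 25% inflation. Section 6.2: 95% confidence intervals, so a two-sided test is taken. Section 3.3: visits at 0, 6 and 12 months.

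**Assumed, not in the SAP.** All between-visit correlations, all follow-up SDs, and 15% missing at month 6 rising to 30% at month 12.

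**Reproducing the plan's figure.** A two-sample t-test with SD 1.4 and difference 0.5 needs 166 per arm. 166 × 1.25 / 0.70 = 296.4, so 297 per arm and 594 in total, as stated. No repeated-measures correlation enters, so 594 does not depend on this point.

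**Formulas, complete data and equal SDs.** Let r01, r12 and r02 be the 0-6, 6-12 and 0-12 month correlations, and R the ratio of model-based to true standard error for the 12-month contrast.

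- Baseline as covariate (rows at 6 and 12 months): R² = ½[(1 − r01²) + (1 − r02²)] / (1 − r02²).
- Baseline as an outcome row (0, 6, 12 months): R² = [1 − (r01 + r12 + r02)/3] / (1 − r02).
- Type I error = 2[1 − Φ(1.96 R)].

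With 0.65/0.65/0.60:
- Covariate: R² = ½(0.5775 + 0.64)/0.64 = 0.951, R = 0.975, type I error 5.6%.
- Row: R² = (1 − 0.6333)/0.40 = 0.917, R = 0.957, type I error 6.1%.

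With 0.80/0.80/0.64:
- Covariate: R² = ½(0.36 + 0.5904)/0.5904 = 0.805, R = 0.897, type I error 7.9%.
- Row: R² = (1 − 0.7467)/0.36 = 0.704, R = 0.839, type I error 10.0%.

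**With 15% and 30% missing.** The compound-symmetry parameters that the model converges to were found by minimising the expected Gaussian deviance over the dropout patterns. The model-based standard error was then compared with the sandwich (true) one.

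| Correlations 0-6/6-12/0-12 | SDs at 0/6/12 | Covariate: R, type I error | Row: R, type I error |
|---|---|---|---|
| 0.60/0.60/0.60 | 1.4/1.4/1.4 | 1.000, 5.0% | 1.000, 5.0% |
| 0.65/0.65/0.60 | 1.4/1.4/1.4 | 0.973, 5.7% | 0.960, 6.0% |
| 0.60/0.65/0.50 | 1.4/1.4/1.4 | 0.958, 6.0% | 0.922, 7.1% |
| 0.70/0.70/0.50 | 1.4/1.4/1.4 | 0.906, 7.6% | 0.861, 9.1% |
| 0.80/0.80/0.64 | 1.4/1.4/1.4 | 0.884, 8.3% | 0.842, 9.9% |
| 0.80/0.80/0.64 | 1.4/1.4/1.6 | 0.838, 10.1% | 0.814, 11.1% |

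In these scenarios the unstructured standard error is 0.99-1.00 times the true standard error of the random-intercept estimator, so the fix loses essentially no real precision.

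**Simulation check.** Random-intercept REML fits with 596 participants, no treatment effect, 30% dropout and correlation decaying by a factor of 0.5-0.8 per six months gave 6.6-8.8% (covariate) and 8.6-10.8% (row), with simulation error of about 1-2 points. Entering baseline as both row and covariate gave 10.9-14.4%.

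**What weakens or reverses the effect (complete data).**
- 18-month rows added, decaying correlation: 5.0-6.1% (covariate) and 6.1-7.9% (row).
- Constant correlation with SDs falling 1.4/1.3/1.2: 4.1% (covariate), slightly conservative.

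**Eligibility limits.** Section 4.1 requires that participants "had persistent hyperglycemia, defined as an A1C between 6.5-12% at baseline (0 months"). A normal distribution with mean 8.5 and SD 1.4 cut to 6.5-12 has SD 1.18. With SDs 1.18/1.4/1.4 and constant correlation 0.60, type I error stays at 5.0% under either handling of baseline.

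**The case against.** The best defence is that every inflated figure above comes from correlations and SDs that the SAP does not state. If correlation is constant and SDs are equal, the planned test is exact. A decay of only 0.05 between the 0-6 and 0-12 month correlations gives 5.6-5.8% with baseline as a covariate. A random-intercept model is a recognised choice, the SAP does not exclude robust standard errors, and section 6.1 commits to checking assumptions. All of this stands, and it rules out saying that the test does run above 5%.

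It does not remove the point. Section 6.1 names no covariance remedy. A structure chosen after looking at the data is not prespecified for the primary test.

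Three stronger readings may tempt a reader.
- That the eligibility limits on baseline A1C themselves break the model. The check shows they do not: selecting on baseline leaves follow-up variance given baseline unchanged, and with baseline as a row the rate stayed at 5.0%.
- That unequal SDs always inflate the error. They can also make the test conservative.
- That a wrong covariance materially biases the estimate under missing at random. This is possible in principle, but nothing in the SAP lets it be sized, and section 6.4 already plans several alternative missing-data analyses.

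**Conclusion.** The within-subject covariance of the primary model is fixed badly. The stated device imposes equal variances and equal correlations over visits, and no named safeguard protects the single-visit primary contrast.

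The size is conditional. Type I error is 5.0% under constant correlation and equal SDs. Under the assumed decay it is about 5.7-8.3% with baseline as covariate (standard error 3-12% too small), and about 6-10% with baseline also an outcome row (4-16% too small). A 12-month SD of 1.6 on top takes the upper end to about 11%. The driver is assumed correlation decay, or an assumed rise in the 12-month SD, and not the eligibility range.

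The higher simulated rates with baseline as both row and covariate are left out of this range. They depend on a separate ambiguity in section 7.4, which describes change from baseline and also adjusts for baseline.

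**What to change.** In section 7.4, for 12-month A1C:

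- Replace the participant random intercept with an unstructured residual covariance over visits, and keep the clinic intercept.
- Name a fallback for non-convergence, for example heterogeneous Toeplitz with robust standard errors.
- State whether baseline A1C is a covariate or an outcome row, not both, and list the visits that enter the model.
- Keep the random-intercept model as a sensitivity analysis.

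Apply the same wording to the other continuous repeated-measures outcomes; the sizes above were worked out for A1C only.

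The cost is a change of SAP text, one model option and a few more variance parameters with about 600 participants. The reported standard error may be slightly larger, which would correct an understatement and not lose information. The sample size of 594 is unaffected.

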6.4 Missing Data

Missing data due to withdrawal or loss-to-follow-up is expected despite mitigation strategies that were in place to reduce missingness. We will examine missing data during cleaning to 1) document potential reasons for missingness, 2) examine the plausibility of a missing at random assumption, and 3) identify auxiliary covariates that may be predictive of outcomes to inform our assumptions and handling of missing data.¹⁰⁹

Missing data will be handled using full information maximum likelihood under a missing at random assumption, provided this assumption appears plausible after examining the data.^{109, 110} Preliminary auxiliary variables, which will be assessed for each outcome, are detailed in Section 7.

To investigate the impact of different assumptions regarding missing data on estimated program impacts, we will use Markov chain Monte Carlo multiple imputation regardless of the percentage of missingness, inverse probability weighting, and available case analysis.¹¹¹⁻¹¹³ We will also use pattern mixture methods models¹¹⁴ to explore the robustness of study findings to the assumption that data are not missing at random.^{109, 115}

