6.6 Statistical Software

Statistical analyses will be conducted in Stata¹¹⁹, and R¹²⁰ using versions specified in the final manuscripts.

7. Analyses

To describe the analyses, we have grouped all outcomes according to the manuscript in which they will be reported. Mixed-effects linear, logistic, and/or non-linear regression models will be used to assess group differences in outcomes at baseline and post-intervention.

The incentive program was paused after 11 weeks due to problems with delivery of the incentive. The incentive program resumed 12 weeks later when the issues were rectified. This restart impacted 31 participants who had completed baseline data collection, been randomized, and begun the program. Those who chose to remain in the program completed baseline data collection a second time, resulting in duplicate baseline measures. The following analyses will include the second set of baseline data unless otherwise specified (i.e., sensitivity analysis).

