7.6 Third Manuscript

This paper will report results for household food insecurity presence and severity (secondary outcome), perceived income adequacy, and subjective social status (exploratory outcomes) at 6- and/or 12-months.

Household Food Insecurity

We will assess group differences in presence of household food insecurity as a binary outcome using mixed-effects logistic regression, and severity of household food insecurity as an ordinal outcome using mixed-effects logistic regression. Models will be adjusted for baseline severity of household food insecurity, and blocking variables (baseline A1C, gender, recruitment location). To improve the precision of effect estimates, models will also be adjusted for age, race/ethnicity, immigrant status, educational attainment, annual household income, home ownership, number of children living in the home, marital status, and diabetes duration. Additionally, all models will include baseline A1C data source (study measured vs administrative health data), and group (FoodRx vs comparison) indicator variables. We will include random intercepts for participants (participant study ID) to account for within-subject correlation due to repeated measures, and for primary care clinics (clinic study ID) to account for clustering of participants within clinics. Missing data for covariates will be addressed using full information maximum likelihood.

We will conduct subgroup analyses for household food insecurity by gender, recruitment location (urban setting, rural setting, Indigenous primary care clinic), Indigenous identity (self-identified as First Nations, Inuk, Métis), baseline A1C (6.5%-8.5%; 8.6%-12%).

We will conduct dose-response analyses to examine whether severity of household food insecurity differs based on the total value of incentives redeemed, a continuous variable, in the first 6 months for the mid-intervention analysis, and in the full 12-months for the post-intervention analysis.

In addition to per-protocol and as-treated analyses, we will conduct sensitivity analyses for household food insecurity to examine the impact on results when food insecurity is modelled as a continuous outcome using mixed-effects linear regression.¹²³

Perceived Income Adequacy

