7.7 Fourth Manuscript

This paper will report results for diabetes-specific PROMs (secondary outcomes) at 12 months, including diabetes self-efficacy, diabetes self-management, diabetes distress, diabetes competing demands, perceived financial barriers to chronic disease care, and hypoglycemic episodes.

Diabetes Self-Efficacy

We will assess group differences in diabetes self-efficacy as a continuous outcome using mixed-effects linear regression. Models will be adjusted for baseline diabetes self-efficacy, and blocking variables (baseline A1C, gender, recruitment location). To improve the precision of effect estimates, models will also be adjusted for age, race/ethnicity, educational attainment, annual household income, years lived in Canada, household composition, marital status, and diabetes duration. Additionally, all models will include baseline A1C data source (study measured vs administrative health data), and group (FoodRx vs comparison) indicator variables. We will include random intercepts for participants (participant study ID) to account for within-subject correlation due to repeated measures, and for primary care clinics (clinic study ID) to account for clustering of participants within clinics. Missing data for covariates will be addressed using full information maximum likelihood.

We will conduct subgroup analyses for diabetes self-efficacy by gender, severity of household food insecurity, recruitment location (urban setting, rural setting, Indigenous primary care clinic), Indigenous identity (self-identified as First Nations, Inuk, Métis), baseline A1C (6.5%-8.5%; 8.6%-12%), and insulin use (yes, any vs no, none).

In addition to per-protocol and as-treated analyses, we will conduct sensitivity analyses for diabetes self-efficacy as described in Section 7.2.

Diabetes Self-Management

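### The SAP relies on full information maximum likelihood for missing covariates, but the mixed models it specifies condition on covariates and it gives no joint model that would deliver this

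*SAP*

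**What the plan says.** SAP 6.4 sets the general rule: "Missing data will be handled using full information maximum likelihood under a missing at random assumption, provided this assumption appears plausible". It adds: "Preliminary auxiliary variables, which will be assessed for each outcome, are detailed in Section 7". As sensitivity analyses it commits to three alternatives, "we will use Markov chain Monte Carlo multiple imputation regardless of the percentage of missingness, inverse probability weighting, and available case analysis", followed by pattern-mixture models.

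SAP 7.4 specifies the primary analysis as a linear mixed-effects regression with participant and clinic intercepts. Beyond the blocking variables it adjusts for age, race/ethnicity, education, number of children at home and diabetes duration. It then says: "Missing data for covariates will be addressed using full information maximum likelihood". The same sentence closes every model description in 7.5 to 7.9 except medication adherence. Those models include logistic and ordinal (7.6, 7.7, 7.9), Tweedie and binomial (7.8) and Poisson (7.9) regressions.

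SAP 6.3 promises an intention-to-treat analysis on all data available. On software, 6.6 says only "Statistical analyses will be conducted in Stata" and R. It names no command, package or estimator.

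Five models in 7.7 adjust for "annual household income, years lived in Canada, household composition, marital status, and diabetes duration", and the financial-barriers model in 7.9 also includes years in Canada. The models in 7.6 instead use "age, race/ethnicity, immigrant status, educational attainment, annual household income".

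**The concern.** Likelihood estimation in a mixed model deals well with missing outcomes: a participant with one visit missing still contributes the others. It does nothing for missing covariates, because the likelihood is written for the outcome given the covariates. To cover covariates by maximum likelihood, they need a distribution of their own, modelled jointly with the outcome. The SAP gives none, although most of the covariates are categorical or counts.

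The auxiliary variables have the same gap. The list in 7.4 for 12-month A1C includes systolic blood pressure, Apo B, BMI or waist circumference, insulin use and household income, none of which is in the primary model. Entered as covariates, they would change the pre-specified model and bring their own missing values.

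Three things are at stake. A participant who lacks one baseline item would lose every visit. For covariates, the primary analysis would become the available case analysis that 6.4 lists as a sensitivity check. And the comparison of multiple imputation with maximum likelihood in 7.4 would compare different sets of participants as well as different methods.

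**Working it through.** **1. The plan's own sample size.** Inputs from SAP 4.2: difference 0.5, SD 1.4, power 90%, type 1 error 5% (taken as two-sided), attrition 30%, inflation 25%.

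- Per arm: 2 × (1.960 + 1.282)² × 1.4² / 0.5² = 164.8, so 165. The t-test version gives 165.7, so 166.
- Inflated: 166 × 1.25 / 0.70 = 296.4, so 297 per arm and 594 in total. This matches the SAP. Starting from 165 gives 590.

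**2. Does a standard mixed model drop the rows?** Data were simulated for 596 participants (299 and 297, SAP 3.4) with two follow-up visits. Outcomes were missing for 15% at 6 months and 30% at 12 months, and one baseline covariate was missing for about 10% of participants.

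- With an observed outcome: 939 rows from 578 participants.
- Used by R nlme (with na.omit): 846 rows from 519 participants. R lme4 also used 846 rows.
- A second simulated set in Python statsmodels, told to drop missing rows, fell from 898 to 821 rows.

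The loss is by participant: one missing baseline value removes all of that person's visits. These fits had a participant intercept only. Neither Stata nor structural-equation routines were run.

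**3. Which covariates are exposed in the primary model?** Gender, recruitment location and baseline A1C were needed for blocking (3.4), and age is an eligibility item (4.1). That leaves mainly race/ethnicity, education, number of children and diabetes duration. The SAP states no missingness rate. If each of the four is missing independently at rate p, the share of participants affected is 1 − (1 − p)⁴: 3.9% at p = 1%, 7.8% at 2%, 11.5% at 3% and 18.6% at 5%. Items skipped together would make the share smaller.

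**4. Effect on power.** With m the assumed share of participants with any missing covariate, and attrition taken as independent of it:

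- effective n per arm = 596 × (1 − m) × 0.70 / 1.25 / 2
- power = Φ(0.5 / (1.4 × √(2/n)) − 1.960)

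| m (assumed) | Randomised and kept | With 12-month A1C | Effective n per arm | Power |
|---|---|---|---|---|
| 0% | 596 | 417 | 166.9 | 90.4% |
| 2% | 584 | 409 | 163.5 | 89.8% |
| 5% | 566 | 396 | 158.5 | 88.9% |
| 10% | 536 | 375 | 150.2 | 87.2% |
| 20% | 477 | 334 | 133.5 | 83.1% |

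**5. Years in Canada.** SAP 4.5 lists it as collected but does not say what value a person born in Canada receives. If it equals age, it largely duplicates a covariate already in those models. If it is blank, it is structurally missing and no missing-at-random method has a true value to recover. Six models use it: five in 7.7 and one in 7.9.

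**The case against.** The strongest reply is that the SAP names no routine. A linear random-intercept model can be written as a structural-equation model with covariates modelled jointly, so the stated method is attainable for the primary analysis. That stands: complete-case analysis is what standard routines would produce, not what the plan prescribes. It does not rescue the non-linear models, where an ordinary mixed fit cannot do what the sentence says.

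A reader might infer that the intention-to-treat sample would shrink silently. The documents do not support that. Available case analysis is listed separately in 6.4, and multiple imputation is planned whatever the amount missing and repeated for the primary outcome in 7.4, so the loss would probably show.

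A reader might also infer a biased treatment effect. Baseline collection preceded randomisation (3.4), so missing baseline items cannot result from allocation. The one qualification is the restart cohort of 31 (Section 7), whose second baseline, taken after randomisation, is the one analysed. They are at most 31/596 = 5.2%.

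The power figures use the unadjusted SD of 1.4, whereas the model adjusts for baseline A1C. With an assumed correlation of 0.3 to 0.5 between baseline and 12 months, power would be about 93% to 96% with nothing lost and about 89% to 94% with 14% lost. The loss is modest either way.

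Finally, a reader might conclude that everyone born in Canada drops out of six models. That depends on questionnaire routing that the SAP does not show.

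**Conclusion.** The point holds as a mismatch between the stated missing-data method and the models specified. The SAP attributes to its mixed regressions a handling of missing covariates that their likelihood does not provide, and supplies neither a joint covariate model nor a route for the auxiliary variables. It is more than a missing detail, because the claim is attached to logistic, ordinal, binomial, Poisson and Tweedie models where the usual fit cannot deliver it, and because two analysts following the text could analyse different sets of participants.

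The size is limited and rests on assumed missingness. At 2% to 20% of participants affected, power in the primary comparison would be about 90% to 83%, against 90.4% with none affected. Provided missingness does not depend on arm, the cost is precision and departure from the full randomised set. The SAP does not establish that the primary analysis will be complete-case, or that the treatment contrast would be biased.

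**What to change.** - Keep the likelihood mixed model for missing outcomes.
- Replace the covariate sentence in 7.4 to 7.9. Impute covariates measured before randomisation, either by the multiple imputation already planned in 6.4 or, in the linear models, by simple mean or missing-category imputation.
- Use multiple imputation for covariates measured at follow-up, such as recall day and usual intake in 7.5.
- Put the auxiliary variables in the imputation model only.
- Reword the third sensitivity analysis in 7.4 to match, since multiple imputation would no longer be contrasted with a likelihood treatment of covariates.
- Report, for each model, numbers randomised against numbers analysed.
- Define the years-in-Canada covariate for people born in Canada, or use the immigrant status variable of 7.6 after confirming that it exists for all participants. It is not listed among the baseline characteristics in 4.5 and may itself be derived from years in Canada.

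The cost is SAP wording and little extra analysis, because multiple imputation is already planned. If the sponsor prefers to keep maximum likelihood for the linear models, the SAP should name the routine and the joint model for covariates and auxiliaries; the non-linear models would still need imputation.
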